Provide a brief description of the study design or data collection methodologies. Details regarding protocol specific research procedures will be discussed in a later section.

Design: A two-arm randomized trial.

Randomization:

- Eligible households with at least one child (reference child) in the BGCAA after-school program whose caregiver/parent (guardian) (reference caregiver) consents to participate in the study will be randomized to either the active intervention or the control (1:1 ratio). Randomization will be stratified by the family's SNAP beneficiary status as SNAP could affect uptake of treatment elements offered in the family support arm.

Blinding: Outcome assessors, principal investigator, and biostatistician are blinded to participant allocation. Participant and other staff are unblinded.

Study arms (19 weeks) (Figure 1):

Randomized arms

Children in both intervention and control arms participate in the BGCAA's after-school program with CATCH curriculum.

1. Across participating school sites, the whole BGCAA's after-school program runs for 3h, Mon-Fri for the school year. Children enrolled are expected to attend a minimum of 2x/week.
2. CATCH curriculum will be delivered as a component of the after-school program in blocks of 45-60 min, twice a week.
3. Children also participate in active recreational time (approx. 60 min, offered 1x/week at a minimum) which consists of a mixture of free play, structured physical activity games, and/or sports activities (including soccer, football, and basketball).

Intervention arm: BGCAA after-school program + Family support

1. Children participate in the BGCAA's after-school program with CATCH curriculum as described above.
2. The child's caregiver will receive the following:
 - Family tip sheets sent via mobile text at the start of the program and then every 3 weeks, to a total of 6 txt messages.
 - Weeks 1-4 (4 weeks):
 - i. Welcome package mailed to the family's residence approximately in the first week of the program.

- ii. Weekly: 1 box of produce
- iii. Recipes accompanying each box (sample recipe card attached to submission)
- iv. Bi-Weekly: Grocery store gift cards (2x \$20, to a total of \$40)
- Weeks 5-19 (total of 10 weeks over the 19-week study timeline):

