Because both the primary and secondary outcome measures are continuous, normally distributed measures, we anticipate having to rely on normal theory analytic methods. Specifically, mixed linear regressions on the primary (HEI) and secondary outcome measures (such as Fruits & Vegetable subscores, BMI and parent HEI) will be fitted to test differential trajectories for two groups from baseline to midpoint and end point assessment of the program, time expressed as days elapsed from baseline. These models readily accommodate differential dropout in the arms with maximum likelihood estimation, random intercepts, and also adjust for any clustering effect of the BGCAA sites. Because randomization will be stratified by whether the family are SNAP recipients or not, the main effect of family's SNAP beneficiary status will be included in all models in addition to the main target terms of interest: two-way interactions of time X treatment, time X SNAP, and their three-way interaction. Overall alpha will be set at 0.05 for each child outcome on these target terms.

In addition to these intention-to-treat (ITT) analyses we will also conduct as-treated (AT) analyses incorporating the 'dose' variable that will be formed based on implementation database elements that permits the tracking of program elements consumed/ picked up/ attended by the target child and his/her parent/guardian in the two active arms. In AT models, total dose taken-up by the end of the program will enter into product terms with time. As is typical, we expect the AT models to have greater sensitivity/ precision in estimating the added value of the family support beyond the elements of the after-school program with CATCH for change in HEI and secondary outcomes. In addition the dose variable sheds light on the effects of Boys and Girls Club programming, including CATCH, regardless of other incentives. Statistical controls for family demographic characteristics, food insecurity, child age, sex, and SNAP beneficiary status will be included in the AT framework as 'dose' is not completely controlled by the randomization and hence would be expected to be correlated with these characteristics (e.g. economically disadvantaged families may be more likely to uptake more of the program elements).

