This integration of height/weight measurements with the after-school day has been agreed to between study and BGCAA staff. Together we wish to minimize the direct and open measurement of weight since it is a sensitive activity for some children. In the experience of BGCAA staff contextualizing it in a more fun and instructional activity (as the above) would reduce the likelihood of causing them unnecessary psychological discomfort while still providing height and weight measurements. During consenting into the study, parents/caregivers will be fully and dully informed about this activity in which their child's weight and height will be obtained.

Interventions

Arm #1 – Intervention arm: BGCAA after-school program + Family support

- Children participate in the BGCAA's after-school program with CATCH curriculum as well as other activities (such as active recreational time that could include sport activities such as soccer, basketball, etc, homework/power hour, and snack time) as they usually do.
- Across school sites, the whole BGCAA's after-school program runs for 2-3h, Mon-Fri. The after-school program happens immediately after school and BGCAA provides transportation from the school to offsite locations if the program is not held at child's school.
- CATCH (<https://catch.org/>) is a school-based program for health education and Whole Child wellness that BGCAA incorporates into their regular activities. BGCAA staff receives training (irrespective of the research) to focus on its healthy eating and healthy movement components. Each site's BGCAA staff will deliver these components over the course of the school semester on the days of the week of their choice, with a minimum frequency of 45-60 min, twice a week.
- Children participate in daily (M-F) recreational time (45-60 min) which consists of a mixture of free play, structured physical activity games, and/or sports activities (including soccer, football, and basketball as examples).

4. The child's parent will receive the following as part of a family support:
 - Approximately every 3 weeks (beginning in Week 1), educational sheets ("tip sheets") will be sent electronically via mobile text messages (total of 6). Sample tip sheet included as an attachment.
 - **1-4 (4 weeks):**

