- Children participate in the BGCAA's after-school program with CATCH curriculum as well as other activities (such as active recreational time, homework/power hour, and snack time)—as described for Arm #1.
- Children participate in daily (M-F) recreational time (45-60 min) which consists of a mixture of free play, structured physical activity games, and/or sports activities (including soccer, football, and basketball).

- They will be attending the same sites as the intervention arm (Arm #1). Hence, they will be exposed to the same after-school content at each participating site.
- The after-school program happens immediately after school and BGCAA provides transportation from the school to offsite locations if the program is not held at child's school.
- At the end of the study, the reference parent will receive \$120 as HEB grocery store gift cards, independently of their end-point measurement being obtained.

SUBJECT POPULATION

12 Protected Subject Populations

Click on the check box (or double click and type an "X" if using Google Docs) each population, if they are specifically studied for this research.

 Active Military Personnel	 Children/Minors	 Decisionally Impaired Adults
 Emancipated Minors	 Fetuses	 Individuals with Limited English Proficiency
 Neonates (Uncertain Viability)	 Neonates (Non-Viable)	 Prisoners
 Pregnant Women	 UT Staff/Employees	 UT Students

13 Research Participant Information

Describe the general characteristics of the subject populations or groups including gender, health status, and any other relevant characteristics. **If you have multiple research populations (e.g., teachers and students), clearly outline characteristics for each group.**

A household will be the subject of randomization, one index parent/caregiver and one index child (parent-child dyads) who meet inclusion criteria will be invited to participate in the research activities (data collection).

Participation in the BGCAA after-school program is governed by that organization according to their mandate.

b Minimum Age

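### Allocation is stratified by SNAP status but not by BGCAA site, so chance site imbalance costs a few per cent of precision that could be kept at little cost

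*Combined protocol and SAP*

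**What the plan says.** **Allocation.** Section 4 (Randomization) sets a 1:1 ratio and says "Randomization will be stratified by the family's SNAP beneficiary status". The reason given is that SNAP could affect uptake of the family support elements. No section stratifies or blocks by site. Section 13 fixes the unit: "A household will be the subject of randomization".

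**Sites.** Sections 13 and 14 refer to 11 sites; the list in section 13 names ten. Both arms are recruited at the same sites. Section 11 says of the control children: "Hence, they will be exposed to the same after-school content at each participating site". Section 11 also lets each site's staff "deliver these components over the course of the school semester on the days of the week of their choice", with a minimum frequency.

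**Analysis.** Section 5 says the mixed models "also adjust for any clustering effect of the BGCAA sites". It does not say whether site is a fixed or random effect, or whether it enters the time slope. Section 15 takes from the 2021 pilot an effect size of .47 with an intraclass correlation of .20 for person x site clusters.

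**Size.** Section 15 gives enrolment scenarios of N=226 and N=150 (96 and 64 per arm after 15% attrition) and a target of 120 retained per arm.

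**The concern.** The plan treats site as a source of correlation in the outcome, both in the model and in the sample size, but does not use it in the allocation. With 11 sites and 150 to 226 households, the average site holds about 14 to 21 families (150/11 and 226/11). Simple chance can then leave a site noticeably uneven between arms. An uneven site gives less within-site information on the treatment effect than an even one of the same size.

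What is at stake is precision and the look of the baseline table. It matters somewhat more here than usual, because recruitment is capped by the partner's capacity. The low scenario in section 15 can detect only d=.60, which is above the pilot effect of .47, so lost information cannot easily be bought back with more families.

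**Working it through.** **1. The plan's own figure.** For d=.47, two-sided alpha .05 (sidedness is not stated) and 80% power, n per arm = 2(1.960+0.842)²/0.47², about 71.1, so 72 without clustering. The plan's 120 needs a design effect of 120/71.1 = 1.69. The other pairs in section 15 (113/.45, 96/.49, 75/.55, 64/.60) imply 1.45 to 1.47. No cluster size is stated, so 120 cannot be reproduced. That is a separate matter, and nothing below depends on it.

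**2. Direction.** With households allocated 1:1 irrespective of site, the expected share of each site is the same in both arms. The site-mix shift in the arm difference therefore has mean zero.

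**3. Size of the chance shift before site adjustment.** Assume 20% of outcome variance lies between sites, reading the stated correlation that way. With J equal sites, the variance of the shift is 0.20 × 4(1−1/J)/(N−1). For J=11:
- N=128 (64 per arm): SD 0.076, 95% of trials within about 0.15
- N=192 (96 per arm): SD 0.062, within about 0.12-0.13
- N=240 (120 per arm): SD 0.055, within about 0.11

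These are in outcome SD units. Simulation of SNAP-stratified allocation (50% SNAP assumed) gives the same values to within rounding.

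**4. Information left after site adjustment, site fixed.** The treatment information is the sum over sites of n₁n₀/n, against N/4 with perfect balance. Under 1:1 allocation that ignores site, the expected ratio is (N−J)/(N−1), whatever the site sizes:
- N=150, J=11: 139/149 = 0.933, a loss of 6.7%
- N=226, J=11: 215/225 = 0.956, a loss of 4.4%
- with the ten named sites: 140/149 = 0.940 and 216/225 = 0.960

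Simulation with SNAP-only stratification agrees: about 0.93 and 0.96, with 5th percentiles of about 0.88 and 0.92.

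**5. Same, site random.** A random site effect recovers some between-site information. With a site share of 0.20, SNAP-only allocation keeps about 95% at N=150 and 96% at N=226. The loss is therefore about 5-7% at N=150 and about 4% at N=226.

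**6. What site stratification recovers.** Blocks of four within site x SNAP (50% SNAP assumed) keep about 99%, not 100%, because small cells leave incomplete blocks. The net gain is about 99−93 = 6 or 99−95 = 4 points at N=150, and 99−96 = 3 at N=226.

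**7. Power at d=.47.** This is a single comparison with fixed-site adjustment and a site share of 0.20. With perfect balance the standard error is √(0.8×4/N), and power is Φ(0.47/SE − 1.96).

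| Retained per arm | SE, SNAP only | SE, site balanced | Power, SNAP only | Power, site balanced |
|---|---|---|---|---|
| 64 | 0.164-0.165 | 0.158 | 81-82% | 84% |
| 96 | 0.132-0.133 | 0.129 | 94% | 95% |
| 120 | 0.118 | 0.115 | 98% | 98% |

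The gain is about 0.5 to 3 points. At the larger sizes it is small partly because power is already near its ceiling. If the design instead sits exactly at 80%, a ratio of 0.933 gives Φ(2.802×√0.933 − 1.96) = 77.2% and 0.956 gives 78.2%, which is within the same range.

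**The case against.** The strongest reply is that randomisation already does the work. Site imbalance is chance, the standard error covers it, and section 5 adjusts for site. Any covariate left out of the stratification could draw the same comment. This stands. It limits the point to a few per cent of precision.

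Three stronger readings are tempting, and the documents support none of them.

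- A reader might infer that the arms receive systematically different background programmes. They do not: households, not sites, are randomised, and both arms attend every site.
- A reader might infer that the same-content statement in section 11 holds only under site stratification. It describes content within each site, and that is true under any allocation of households.
- A reader might take the differing descriptions of programme length and recreation time in sections 4 and 11 as evidence that sites differ. Section 11 gives both arms the same recreation schedule, so that difference looks like inconsistent wording between sections. Choice of days for CATCH need not change how much is delivered. The .20 correlation comes from a pilot with curbside distribution and says little about after-school delivery here.

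Nor is it useful to count how often some site splits 70:30 or worse. That frequency depends on assumed site sizes (a four-family site splitting 3:1 would count), and it measures neither bias nor power.

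The reply does not remove the precision loss. Adjustment handles site differences in the outcome, but it cannot restore within-site information lost to uneven splits.

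**Conclusion.** The point holds as a modest precision improvement. SNAP-only allocation costs about 5-7% of the effective sample at N=150 and about 4% at N=226 after site adjustment. Adding site recovers about 3-6% on average, or roughly 0.5-3 points of power, most in the low-enrolment scenario. There is no systematic bias and no contradiction within the plan.

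The average fixed-site loss depends only on N and the number of sites. The rest relies on assumptions that the documents do not settle: a between-site variance share of 0.20, a 50% SNAP share, site sizes and block size. The power figures are for a single comparison, whereas the target term in section 5 is time x treatment. A site intercept alone would adjust for level but not for site differences in change, and balance by design does not depend on how that is modelled.

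**What to change.** In section 4 (Randomization), add BGCAA site as an allocation factor alongside SNAP status. Use small, randomly varying blocks within site x SNAP cells, or minimisation on both factors with a random element if some cells are sparse. Keep site and SNAP in the section 5 models, and state there how site enters (fixed or random, and whether with time).

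The cost is a change to the allocation list before enrolment. Site is among the fields collected on the interest form (section 17), so it is available before randomisation. The downside is some incomplete blocks in small cells, which minimisation avoids, and slightly more work in preparing and running the list.

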Study Procedure Description	Benefits	Compensation & Costs
Subject Population	Risks	

GENERAL STUDY INFORMATION

Study Title

Include the study title below.

FUEL: Food, fUn, frEsh, famiLy program. Promoting children's diet through afterschool program and family support.

1 Review Type (Choose one)

Please choose which level of review best fits your research. This is an investigator's assessment of review and does not preclude the IRB from alternate determinations. In cases where the investigator and the IRB's determination of review conflict, the IRB's determination will be considered the official determination.

Note: Expedited review does not refer to the timeliness of the review of your protocol, but specific categories of research defined by OHRP. If you would like help determining which type of review best fits your research study, please contact the IRB staff in the Office of Research Support & Compliance:

<https://research.utexas.edu/ors/human-subjects/get-help/>

a **Full Board Review – Greater than Minimal Risk Research**

b **Expedited Review – Minimal Risk Research**

2 Research Hypotheses

Please describe the research aims and hypotheses in the box below. To input text, click in the box below and start typing.

Note: Procedures will be explained in a separate section below.

Our primary hypothesis is that the effect of an after-school curriculum on nutrition and physical activity for elementary aged children improves overall child diet better when resources to encourage healthier eating are provided to caregivers at the same time than if they are not provided.

3 Study Background

Provide the rationale and the scientific or scholarly background for the proposed activity, based on existing literature (or clinical knowledge). Describe the gaps in current knowledge that the project is intended to address.

One approach to improving child health trajectories including diet has focused on after-school programming. A prominent example, the “Coordinated Approach to Child Health” (CATCH) program, provides curriculum on nutrition and physical activity. CATCH has, over almost two decades of implementation and assessment, shown positive impacts on reducing the incidence of obesity and improving child diet (Hoelscher et al, 2010). It is regularly used by organizations such as the Boys and

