 - i. For five weeks, an optional online form (or “*goal sheet*”) will be sent to the parent/caregiver (5 sheets in total) with questions about trying new FV items to be completed within the next 7 days. As an incentive, a \$10 gift card will be sent the following week to those who complete it (a potential total of \$50).
 - ii. Week 11: \$20 Grocery store gift card. Based on disruptions due to the school year breaks, we will provide an extra \$20 gift card to re-engage the week after a school holiday.

Control arm: BGC after-school program only

1. Children participate in the BGCAs after-school program with CATCH curriculum as described above.
2. At the end of the study, they will receive \$120 as grocery store gift cards.

[figure not shown]

Figure 1. Study design: 2 randomized arms

Outcomes:

- Primary:
 - Child's diet quality: measured by Healthy Eating Index, HEI, scores calculated from the Texas School Physical Activity and Nutrition (SPAN), 2nd Grade.
 - Child's fruits and vegetable consumption, measured by SPAN, 2nd Grade.
- Secondary outcomes:
 - Caregiver/parent diet quality, measured by HEI scores calculated from the SPAN, 8th Grade.
 - Child's physical activity levels
 - Child's body mass index, as percentile of BMI-for-age

Study measurements:

Timepoint measurements for all study participants (child-parent dyads) include:

- baseline (approximately up to 4 weeks prior to the first produce bag and grocery store gift card being distributed). Height and weight will be taken during the first 1-2 weeks of the research program start date during a BGCAA field day.
- mid-point (planned for approximately weeks 5-8)
- end-point (approximately between weeks 16 and 21). Height and weight will be taken during the 19th week of the program at the BGCAA's field day.

Outcomes	Tool	Time points	Administration
Child's Diet (primary)	TX SPAN 2 nd grade 2019-2020 – Dietary questions	Baseline, Mid-point, End point	Child, Guardian-reported Structured interview over the phone by RA
	SPAN Healthy Eating Index scores (includes total, healthy, and unhealthy scores)	Baseline, Mid-point, End point	Child, calculated from SPAN
Physical Activity	TX SPAN 2 nd grade 2019-2020 – Physical activity questions	Baseline, End point	Child, guardian-reported Structured interview over the phone by RA
	Physical Activity Questionnaire – Children		

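### Child fruit and vegetable consumption is primary in section 4 but secondary in section 5, and no rule says whether it can carry the primary claim if HEI does not

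*Combined protocol and SAP*

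**What the plan says.** The status of the fruit and vegetable (FV) outcome depends on where one reads.

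- **Section 2, Research Hypotheses.** There is one primary hypothesis: the after-school curriculum "improves overall child diet better when resources to encourage healthier eating are provided to caregivers". FV is not named.
- **Section 4, Outcomes.** Two bullets stand under the primary heading: child diet quality by HEI, and child "fruits and vegetable consumption, measured by SPAN, 2nd Grade". FV does not appear in the secondary list. The measures table marks the whole child-diet block as primary, and that block holds both the SPAN dietary questions and the HEI scores (total, healthy and unhealthy).
- **Section 5, Data Analysis.** The models are "mixed linear regressions on the primary (HEI) and secondary outcome measures (such as Fruits & Vegetable subscores, BMI and parent HEI". The as-treated paragraph repeats the division: "for change in HEI and secondary outcomes".
- **Section 5, tests and alpha.** The models are fitted "to test differential trajectories for two groups from baseline to midpoint and end point assessment". The plan gives as "main target terms of interest: two-way interactions of time X treatment, time X SNAP, and their three-way interaction". On error control it says: "Overall alpha will be set at 0.05 for each child outcome on these target terms". The only correction for multiple testing is in the exploratory dose analyses.
- **Section 15, Sample size rationale.** The between-arm calculation uses overall child HEI only.

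**The concern.** The two sections disagree on what counts as success. The intervention supplies produce boxes and pays for goal sheets about produce, so FV is the outcome closest to it. A significant FV result beside a null HEI is a plausible finding. Section 4 would let it be reported as a positive primary result; section 5 would not. With no rule written down, the choice could be made after the data are seen.

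A second gap sits on top of this. Section 5 names three target terms and does not say which one answers the hypothesis, although section 2 and the stated aim of comparing trajectories between the groups point to time by treatment.

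**Working it through.** **The passages side by side.** HEI is primary in both sections. FV is primary in section 4 and secondary in section 5. I take the FV consumption of section 4 and the FV subscores of section 5 to be the same SPAN-derived measure; the plan does not define either. The section 5 alpha sentence may limit error across the terms within one outcome. It does not limit error across outcomes on any reading.

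**Inputs.** From section 5: alpha .05 per child outcome. From section 15: 80% power, d = .47 and 120 retained per arm, plus the four scenario pairs of n and d. My assumptions: two-sided tests (sidedness is not stated), test statistics jointly normal across outcomes, the correlations shown, and equal power for FV where joint power is given.

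**The plan's own sample size.** Without clustering, n per arm = 2 × (1.960 + 0.842)² / 0.47² = 71.1. The stated 120 implies a design effect of 120 / 71.1 = 1.69. The scenarios imply n / [2 × (2.802/d)²]:

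| n per arm | d | implied design effect |
|---|---|---|
| 113 | .45 | 1.458 |
| 96 | .49 | 1.468 |
| 75 | .55 | 1.445 |
| 64 | .60 | 1.468 |
| 120 | .47 | 1.689 |

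The 120 does not follow from the design effect behind the scenarios, and the cluster size is not given. The present point does not depend on this, but power is shown both ways below.

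**If either outcome suffices.** With one .05 test per outcome and both nulls true, the chance of at least one false claim is 1 − P(|Z1| < 1.96 and |Z2| < 1.96). Under independence this is 1 − .95² = .0975.

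**If both must succeed.** There is no inflation. With 80% power for each, joint power is .80² = .64 under independence and higher with positive correlation.

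| correlation | false primary claim, either suffices | joint power, both required |
|---|---|---|
| 0 | .0975 | .640 |
| .5 | .091 | .687 |
| .7 | .083 | .713 |
| .9 | .070 | .750 |

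Under the scenario design effect (1.45 to 1.47), HEI power at 120 per arm and d = .47 is Φ(.47 × √(120 / (2 × 1.46)) − 1.960) = Φ(3.013 − 1.960), about 85%. If FV had the same power, joint power would be about 73% at correlation 0 and about 81% at .9.

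**If more than one term may carry the claim.** With two independent terms for each of two independent outcomes, all at .05, the error is 1 − .95⁴ = .185. This is a conditional example, not a reading that the plan states.

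**If both stay primary with Bonferroni.** The critical value at .025 is 2.241. If 120 per arm gives exactly 80% at .05, HEI power becomes Φ(2.802 − 2.241) = 71%. Under the scenario design effect it is Φ(3.013 − 2.241) = 78%.

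**The case against.** The strongest reply is that the plan mostly settles the matter itself. It has one hypothesis about overall diet, the analysis section calls HEI the primary, and the between-arm sizing uses HEI alone. On that reading the error rate stays at .05 and only a bullet in section 4 is misplaced. This is a good reason to choose HEI, but it does not remove the conflict: section 4 holds the formal outcome list, and nothing gives section 5 precedence. Section 3 also reports that the pilot improved FV intake, so an intended FV primary cannot be ruled out.

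It can also be said that consumption and subscores may be different measures. The plan does not exclude this. If they differ, a listed primary outcome has no named analysis in section 5, and that also needs correcting.

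Two supporting places are weaker than the rest. The measures table does not name FV, and its SPAN row is also the source of the HEI scores. The as-treated sentence does not name FV either. The conflict rests mainly on the section 4 bullet against the section 5 parenthesis, and that is enough.

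Finally, .185 depends on independent terms. With 0/1 coding and equal SNAP strata (both assumed), the time by treatment and three-way terms correlate at about −.71. The figure is then about .16 with independent outcomes. That limits the example and leaves the two-outcome figures unchanged.

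**Conclusion.** The concern holds and must be fixed before analysis. Sections 4 and 5 classify FV differently, and no success rule links the outcomes. If either suffices, the false-claim rate lies between .070 and .0975 for correlations from .9 to 0, against a nominal .05. If both are required, joint power falls to between 64% and 75% when each has 80%. The correlations, two-sided testing and equal FV power are assumptions; the plan gives none of them. The contradiction itself needs only the assumption that the two FV labels mean the same measure, and a defect remains if they do not.

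**What to change.** In section 4, make child total HEI the sole primary outcome and move FV consumption to the secondary list, optionally tested at .05 only if HEI succeeds. Naming the total score matters because the measures table also lists healthy and unhealthy scores, while section 15 is sized on overall HEI. In section 5, state that the time by treatment contrast for HEI carries the primary claim at .05, and that time by SNAP and the three-way term do not. Use one name for the FV measure throughout.

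This costs a change of wording in section 4 and a sentence or two in section 5; the sample size stands. The price is that FV cannot support a confirmatory claim if HEI fails.

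If both outcomes are to stay primary, state whether one or both must succeed. If one suffices, use Holm or Bonferroni. Under Bonferroni, HEI power at 120 per arm is about 71% or 78%, depending on which of the two implied design effects applies.
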